5.2 Subject Selection

The target population includes patients who have received breast cancer therapy and developed unilateral lymphedema secondary to their cancer treatment. Patients will be recruited from the clinical investigator's patient population.

5.2.1 Inclusion Criteria:

1. Female 18 years of age or older
2. Diagnosis of unilateral breast cancer-related lymphedema
3. Stage I or early stage II lymphedema without severe fibrosis at the time of enrollment
4. $\geq 5\%$ volume difference between affected and unaffected arm as verified via perometry (LymphaTech 3D scanner)
5. Willing and able to give informed consent
6. Willing and able to comply with the study protocol requirements and all study-related visit requirements

5.2.2 Exclusion Criteria:

1. In-home use of PCD within previous 3 months
2. Therapist or self-administered manual lymph drainage (MLD) within previous 1 week
3. Mastectomy or lymph node removal on side without lymphedema
4. Bilateral lymphedema
5. Heart failure (acute pulmonary edema, decompensated acute heart failure)

6. Acute venous disease (acute thrombophlebitis, acute deep venous thrombosis, acute pulmonary embolism)
7. Active skin or limb infection/inflammatory disease (acute cellulitis, other uncontrolled skin or untreated inflammatory skin disease) on the arms or trunk
8. Active cancer (cancer that is currently under treatment, but not yet in remission)
9. Poorly controlled kidney disease (glomerular filtration rate < 30 mls per minute), hypoproteinemia, pulmonary hypertension, hypothyroidism, cyclic edema, or Munchausen Syndrome
10. BMI >50
11. Any circumstance where increased lymphatic or venous return is undesirable
12. Currently pregnant or trying to become pregnant
13. Allergy to iodine

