8.0 Study Procedures

8.1 Informed Consent

Subjects will need to sign an informed consent form that has been approved by both the Sponsor and reviewing IRB to be considered for participation in this study. Subjects must meet all of the inclusion and none of the exclusion criteria.

Each subject (or a legally authorized representative) must give written consent, in accordance with local requirements, after the nature of the study has been fully explained and questions answered. The consent form must be signed prior to any study-related procedures, and the process of informed consent must be documented in the subject's record.

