8.2 Demographics & Medical History

Demographics will be collected including the age at time of participation, ethnicity, race, and sex.

Significant medical history, including lymphedema history, will be collected.

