8.9 ICG Injections

ICG (25 mg vial) will be reconstituted with 10 ml sterile water provided by the manufacturer; further dilutions will be made in saline to achieve the final concentration of 0.32 ml, or 250 µg/ml ICG. Up to 16 intradermal injections, each consisting of 0.1 mL or less, using conventional 30 or 31-gauge needles may be administered by a clinician. However, typically each subject will only receive 8 intradermal injections in the arms and the additional 8 injections may be administered if the clinician identifies areas of lymphatic drainage that may not be covered by the typical injections. Subjects will typically receive 2 injections in the

dorsum of each hand and 2 in each medial wrist. Subjects will not receive more than 400 µg of ICG.

Vital signs (blood pressure, heart rate, temperature) and redness or inflammation at the injection sites will be monitored and recorded at baseline (pre-injection of ICG) and at 15 and 30 minutes after the initial injection. Study subjects will be contacted between 18 and 28 hours after ICG administration to ensure no adverse events have occurred

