8.13 Randomization

If the subject meets all of the inclusion criteria and none of the exclusion criteria, they will be randomly assigned to FT or FT-SW. The appropriate unblinded staff

member will obtain the randomization assignment by entering the appropriate randomization CRF in the EDC system.

The randomization assignment cannot be changed or chosen by the subject or the investigator.

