11.1.2 NIRF Imaging

Participants may have an allergic reaction to ICG that can include itchiness and/or swelling; there is a rare possibility of a severe reaction, including death. Two anaphylactic deaths have resulted from IV injection of ICG at the maximal approved dose (2 mg/kg). Because we will inject a maximum dose of 400 µg of ICG, the risk of severe adverse event is extremely low. Members of the research team will be present during the entire imaging procedure and physicians will be nearby to provide antihistamines or other interventions if needed. To minimize discomfort from intradermal injections, subjects may have a topical anesthetic agent (ethyl chloride spray) applied to the injection sites prior to administering ICG.

To generate the fluorescent signal for NIRF imaging, the subject's arms and sides will be illuminated with the diffused output of a 785 nm laser diode. Risks associated with Class IIIB/IV lasers are not applicable for this study, since the fluence rate at which the laser diode is operated (≤ 1.9 mW/cm²) constitutes no skin hazard. However, participants will be instructed in general laser safety precautions as applicable to their participation and will be required to wear laser safety goggles during NIRF imaging. Additional laser safety goggles will be available for other individuals in the room if they wish to wear them.

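### The risk section names indocyanine green (ICG) as the allergen, but the only allergy exclusion is iodine, so the written criteria admit a woman with a known ICG reaction

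*Combined protocol and SAP*

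**What the plan says.** Section 11.1.2 (NIRF Imaging) states that "Participants may have an allergic reaction to ICG" and that "there is a rare possibility of a severe reaction, including death". It cites two anaphylactic deaths after intravenous ICG at 2 mg/kg and, because the dose here is at most 400 µg, concludes that "the risk of severe adverse event is extremely low".

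The exclusion lists in the synopsis and in section 5.2.2 agree. Each has 13 items, and the only one about allergy is item 13: "Allergy to iodine".

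On who enters, section 5.3 counts a subject as enrolled once consent is signed and all criteria are met. Section 8.1 says "Subjects must meet all of the inclusion and none of the exclusion criteria", and section 8.13 repeats the condition for randomisation ("If the subject meets all of the inclusion criteria and none of the exclusion criteria").

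On screening, section 6.1 lists medical history ahead of the ICG injections. Section 8.2 describes its content: "Significant medical history, including lymphedema history, will be collected". Neither section mentions allergy or previous ICG exposure.

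**The concern.** The eligibility rule and the risk section name different substances. ICG is given purely as a study procedure, for investigational imaging, so the person most plainly at risk is someone who has already reacted to it. An exclusion list should stop that person before exposure.

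Elsewhere the protocol does match hazard to exclusion. Section 11.1.1 describes the fluid shift caused by compression and points to the exclusion of heart failure. Pregnancy is excluded, and section 6.1 times the pregnancy test relative to imaging. For ICG allergy the hazard is named but the matching exclusion is missing. What is at stake is a foreseeable and avoidable exposure, with an outcome that the protocol itself says can, rarely, be fatal.

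**Working it through.** The plan gives no figure to reproduce on this point. The check is a reading of the criteria and safeguards, followed by simple dose arithmetic to size the issue.

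**1. Does any other criterion cover a known ICG reactor?** The other twelve exclusions are:

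- 1 and 2: recent pneumatic compression or manual drainage.
- 3 and 4: surgery on the other side, and bilateral disease.
- 5 to 9: heart failure, acute venous disease, active skin or limb infection or inflammatory disease, active cancer, and a list of kidney and other conditions.
- 10: body mass index.
- 11: circumstances in which more lymphatic or venous return is unwanted.
- 12: pregnancy.

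None concerns allergy. Items 7 and 11 come closest, but 7 is about active disease and 11 about fluid return. There is no general exclusion for unsuitability in the investigator's opinion. Inclusion 6, on willingness and ability to comply, could be stretched to cover the case, but it prompts nobody to ask about ICG.

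**2. Does any procedure close the gap?**

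| Safeguard | Section | When it acts | Stops a known reactor? |
|---|---|---|---|
| Medical history | 6.1, 8.2 | Before injection | Only if she or the clinician raises it |
| Clinician gives the injections | 8.9 | At injection | By judgment; no rule |
| Investigator may withdraw a subject | 9.0 | Any time | By judgment; not an eligibility rule |
| Dose cap of 400 µg | 8.9, 11.1.2 | At injection | No; limits the dose |
| Team present, physicians nearby with antihistamines | 11.1.2 | During imaging | No; responds to a reaction |
| Vital signs and injection sites checked "at 15 and 30 minutes after the initial injection" | 8.9 | After injection | No |
| Contact at 18 to 28 hours | 6.5, 8.9 | After injection | No |

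**3. Dose per subject.** Section 3.2.3 gives 25 µg in 0.1 cc, which is 25 / 0.1 = 250 µg/mL, the concentration in section 8.9.

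- Typical: 8 injections × 0.1 mL × 250 µg/mL = 200 µg.
- Maximum: 16 × 0.1 mL × 250 µg/mL = 400 µg = 0.4 mg, which matches the stated cap.

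**4. Comparison with the cited deaths.** Those followed 2 mg/kg intravenously. The protocol gives no body weights, so these are assumed.

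| Assumed weight | Intravenous dose at 2 mg/kg | Ratio to 0.4 mg |
|---|---|---|
| 50 kg | 100 mg | 250 |
| 70 kg | 140 mg | 350 |
| 100 kg | 200 mg | 500 |

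The cap is thus far below the dose in those cases. That supports a low risk for subjects in general. The protocol offers no information on someone who has already reacted.

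**5. Overall exposure.** With 20 subjects and up to 5 replacements, the count runs from about 20 × 8 = 160 to 25 × 16 = 400 injections. These are not strict bounds, because injection precedes randomisation and a replaced subject may have left before being injected. They describe exposure of the whole cohort. The number of prior reactors is not known.

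**The case against.** The best reply is that this is incomplete wording of a safeguard that already exists. Nothing else in the study gives an evident reason to exclude iodine allergy, so exclusion 13 was probably written with ICG in mind. The imaging runs under an existing IND, which section 3.2.3 says has covered hundreds of patients without adverse effects. The IND documents, consent form or case report form may already ask about ICG, and they are not available here. Patients come from the investigator's own practice, the study is explained before any procedure, history precedes injection and a clinician injects. For harm to follow, a woman would have to stay silent about a known reaction, or a clinician would have to inject her regardless.

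Much of this stands. It makes the event unlikely, and it means the text permits the injection but does not compel it. It does not change the reading of the criteria. If iodine is a proxy for ICG, the protocol does not say so, and a proxy would still miss a woman who reacts to ICG but not to iodine. The experience under the IND is not said to include anyone with a previous reaction. Section 8.13 is weak support for the concern, since randomisation comes after the injections. The enrolment rule in section 5.3 carries the point without it.

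**Conclusion.** The concern holds. Read literally, the criteria allow enrolment and injection of a woman with a known ICG reaction and no iodine allergy, and nothing in the protocol requires anyone to ask. Apart from the dose cap, the written safeguards rely on clinical judgment or act during or after the injection.

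The practical size is small. Prior reactors in a study of 20 to 25 women are likely to be very few, the dose is low, and no endpoint, analysis or sample size is affected. The correction is still worth making, because the rule names a different substance from the protocol's own stated hazard, that hazard includes death, and the change is almost free. The conclusion rests on the protocol text alone. If the case report form, consent form or IND already contains the check, the amendment simply brings the protocol into line.

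**What to change.** Reword exclusion 13, in both the synopsis and section 5.2.2, to: *Known allergy or previous reaction to ICG, or allergy to iodine.* The inclusion/exclusion assessment already scheduled at screening would then force the check.

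Add one question on previous ICG exposure and any reaction to the medical history in sections 6.1 and 8.2, to be answered before the injections. This is secondary, since the reworded criterion does most of the work, but it makes the answer a documented one.

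The cost is a few words in two places and one history item. No visit or procedure is added, and essentially no recruitment is lost.

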5.3 Point of Enrollment and Randomization

Subjects will be considered enrolled in the study once the Informed Consent Form is signed and all inclusion/exclusion criteria are met. The investigator will keep a record, the subject screening log, of subjects who enter screening. Any subjects who do not meet inclusion/exclusion criteria will be considered screen failures.

Randomization codes will be generated by a Statistician in a permuted block design. The block size will be balanced within each block and will maintain a 1:1 ratio between the treatment groups. The randomization assignment will be obtained from the database and assigned sequentially as soon as an eligible subject completes the pre-treatment measurements.

If a subject does not meet all the eligibility criteria or meets any of the exclusion criteria but is randomized in error, or incorrectly started on treatment, the Investigator should inform Tactile Medical immediately.

Up to 5 enrolled subjects may be replaced if the subject is withdrawn prior to completion of the study. If a subject withdraws from participation in the study, his or her randomization code cannot be reused.

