Inclusion/Exclusion	
Inclusion Criteria:
 
 Female 18 years of age or older Diagnosis of unilateral breast cancer-related lymphedema Stage I or early Stage II lymphedema without severe fibrosis at the time of enrollment ≥ 5% volume difference between affected and unaffected arm as verified via perometry (LymphaTech 3D scanner) Willing and able to give informed consent Willing and able to comply with the study protocol requirements and all study-related visit requirements 
Exclusion Criteria:
 
 In-home use of pneumatic compression device (PCD) within previous 3 months

	
 2. Therapist or self-administered manual lymph drainage (MLD) within previous 1 week 3. Mastectomy or lymph node removal on side without lymphedema 4. Bilateral lymphedema 5. Heart failure (acute pulmonary edema, decompensated acute heart failure) 6. Acute venous disease (acute thrombophlebitis, acute deep venous thrombosis, acute pulmonary embolism) 7. Active skin or limb infection/inflammatory disease (acute cellulitis, other uncontrolled skin or untreated inflammatory skin disease) on the arms or trunk 8. Active cancer (cancer that is currently under treatment, but not yet in remission) 9. Poorly controlled kidney disease (glomerular filtration rate < 30 mls per minute), hypoproteinemia, pulmonary hypertension, hypothyroidism, cyclic edema, or Munchausen Syndrome 10. Body Mass Index (BMI) >50 11. Any circumstance where increased lymphatic or venous return is undesirable 12. Currently pregnant or trying to become pregnant 13. Allergy to iodine
Treatment Duration	
A single treatment lasting:
 
 • FT-SW: Approximately 40 minutes OR • FT: Approximately 60 minutes
Number Planned	20 subjects randomized (minimum of 10 in each arm) with replacement of up to 5 early withdrawals.

TABLE OF CONTENTS

1.0	Contact Information	7
1.1	Sponsor Contact Information.....	7
1.2	Principal Investigator Information.....	7
1.3	Clinical Investigator Information	7
2.0	Abbreviations	8
3.0	Introduction.....	10
3.1	Background and Rationale.....	10
3.2	Device Description	10
4.0	Study Objective.....	13
5.0	Study Design.....	13
5.1	Endpoints	13
5.2	Subject Selection	14
5.3	Point of Enrollment and Randomization	15
5.4	Treatment Assignment and Duration.....	15
5.5	Study Timeline	15
6.0	Study Assessments.....	15
6.1	Screening/Baseline	16
6.2	Randomization.....	16

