3.0 Introduction

3.1 Background and Rationale

Lymphedema is a chronic debilitating disease marked by accumulation of protein rich fluid in the interstitium of the skin (1). This insufficiency in the lymphatic system leads to limb edema in early stages and progresses to thickened skin or fibrosis over time. As a result, persons afflicted with lymphedema are prone to develop impaired extremity function, recurrent episodes of soft tissue inflammation and infection, lymphorrhea, unsatisfactory cosmesis, and a variety of psychological and social issues (2).

Lymphedema may be inherited (primary) or caused by injury to the lymphatic vessels (secondary). While the exact cause of primary lymphedema is unknown, it generally occurs due to congenital malformations with the onset of symptoms presenting at birth, during puberty, or well into adulthood. Secondary lymphedema typically results from trauma to the lymphatic system, surgery, radiation therapy, obesity, and chronic venous insufficiency (3-4). Breast Cancer-Related Lymphedema (BCRL) is a common complication from breast cancer treatment, with reported frequencies ranging from 6% to 65% (5).

There is currently no cure for lymphedema, thus treatment focuses on symptom management and improved patient-reported outcomes. Using a multimodal approach, accepted interventions include: limb elevation, manual lymphatic drainage, compression therapy, skin hygiene, and in very severe cases, lymphatic exchange (6). Pneumatic Compression Devices (PCDs) are a fairly recent addition to the armamentarium clinicians offer patients in the treatment of lymphedema. Studies have demonstrated continual use of PCDs is associated with a significant patient-reported improvement in overall symptoms, decreased limb-girth, decreased limb volume, increased elasticity of tissues, and fewer episodes of infection (7-10).

The efficacy of PCD therapy depends on the applied force (pressure) mobilizing stagnant edema fluid, time of compression to move fluid to the root of the limb, and elasticity of skin and subcutaneous tissue. Thus, adherence to prescribed, at-home self-care is a critical factor in the treatment of lymphedema (11-12). One of the most robust findings in adherence literature concerns aspects of the therapy itself – the more complex and complicated a therapeutic regimen is (e.g., treatment duration), the less likely patients are to adhere to all aspects of prescribed care (12).

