8.5 Subject Surveys

Prior to treatment the subject will complete the ESAS-R. After treatment and assessments are completed, the subject will complete the ESAS-R and a Treatment Perception survey.

8.6 **Lymphedema Evaluation**

Research personnel will confirm the presence of Stage I or early Stage II lymphedema and severity of fibrosis at Screening/Baseline. The clinical stage of lymphedema will be evaluated by a clinician using the following definitions:

- Stage 0: Latent – No clinical signs (no evident swelling)
- Stage 1: Soft swelling (pitting) that resolves with elevation
- Stage 2: Spongy swelling (pitting and non-pitting) that does not resolve with elevation; fibrosis may or may not be present
- Stage 3: Symptoms of lymphostatic elephantiasis where pitting is absent and trophic skin changes develop; extensive fibrotic swelling, blistering, ulceration, lymphorrhea, papilloma, and/or recurrent infections may be present

Severity of fibrosis, to distinguish between early and late Stage II lymphedema, will be based on the definitions below:

Table 3. Fibrosis Assessment

None	No fibrotic tissue
Minimal	Able to move skin parallel to plane (sliding) and perpendicular to skin (pinching up), <20% of affected limb noted to have fibrotic tissue
Moderate	Able to slide skin, unable to pinch skin, 20-40% of affected limb noted to have fibrotic tissue
Severe	Unable to slide or pinch skin, >40% of affected limb noted to have fibrotic tissue

8.7 **Perometry**

Perometry will be performed on both limbs before and after treatment. The LymphaTech 3D Scanner will be utilized by appropriately trained research personnel in accordance with the instructions for use provided by LymphaTech.

8.8 **Marking Anatomical Sites**

Have the subject pull-up/remove clothing if covering arms. Using a pen or marker, with the subject in a seated or standing position with arms completely relaxed at sides, mark the skin at the locations outlined in Figures 3-5 on affected and unaffected sides.

If a subject experiences pain at a targeted measurement site, an alternate location may be measured, recorded, and used for the duration of the study.

[figure not shown]

Figure 3. Site A is on the anterior forearm 6 cm below (distal to) the midline of the antecubital fossa.

Figure 4. Site B is 6 cm above (proximal to) the dorsal aspect of the wrist (midline).

Figure 5. Site C is 3 cm distal to the midline dorsal aspect of the wrist.

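### The arm comparison uses neither baseline values nor lymphedema stage, although both are recorded before randomisation; adjusting for them is a cheap improvement in a trial of 20

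*Combined protocol and SAP*

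**What the plan says.** Eligibility (section 5.2.1) admits "Stage I or early stage II lymphedema without severe fibrosis at the time of enrollment". Section 8.6 separates the two stages by reversibility: "Stage 1: Soft swelling (pitting) that resolves with elevation", against "Stage 2: Spongy swelling (pitting and non-pitting) that does not resolve with elevation; fibrosis may or may not be present". The same section fixes when this is assessed: "Research personnel will confirm the presence of Stage I or early Stage II lymphedema and severity of fibrosis at Screening/Baseline". Sections 6.1 and 6.2 place baseline volume, local tissue water and skin thickness before randomisation as well.

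On allocation, section 5.3 states "Randomization codes will be generated by a Statistician in a permuted block design", at 1:1, with no stratification factor. Sections 6.2 and 8.13 add none. The synopsis plans "20 subjects randomized (minimum of 10 in each arm) with replacement of up to 5 early withdrawals".

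On analysis, Table 1 lists the proportions of subjects who improve and the mean changes from before to after treatment. Section 16 gives descriptive statistics for continuous variables, and percentages with 95% CIs for categorical ones. It plans no formal tests. It names no covariate, no split by stage and no interval for a between-arm difference in a continuous outcome.

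**The concern.** The objective in section 4.0 is to show that the two devices are equivalent, and no margin is given. Readers will therefore judge similarity from the arm estimates themselves. With about 10 per arm, permuted blocks balance the number of subjects but not their characteristics.

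Two recorded characteristics could matter. The first is the baseline value: an arm that starts with more fluid has more to lose, and a simple change score does not remove that dependence. The second is stage, since swelling that resolves with elevation may respond differently to one session from swelling that does not. Section 3.1 also says that the efficacy of compression depends on applied pressure, "time of compression to move fluid to the root of the limb, and elasticity of skin and subcutaneous tissue". If the arms differ by chance on either characteristic, the raw comparison partly reflects who was allocated where, and no planned display would show it.

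**Working it through.** **Plan's own figure.** The planned 20 has no power or precision calculation behind it. The only check available is 2 x 10 = 20, which agrees.

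**Inputs.** N = 20, arms of 10 (synopsis). Two stages admitted (5.2.1). No stratification (5.3). The documents give neither the stage mix nor any effect of stage on response, so both are assumptions shown over ranges.

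**Step 1: chance imbalance in stage.** With K Stage I subjects among 20 and 10 per arm, the number x in one arm is hypergeometric: P(x) = C(K,x) C(20-K,10-x) / C(20,10). The arms differ by |2x - K|.

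| K (Stage I of 20) | P(difference of 4 or more) |
|---|---|
| 6 or 14 | 14.1% |
| 8 or 12 | 17.0% |
| 10 | 17.9% |

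For odd K the difference must be odd, so 4 or more means 5 or more, and the probability is lower:
- K = 7 or 13: 2 x (286 + 5,005) / 184,756 = 5.7%.
- K = 9 or 11: 2 x (11 + 495 + 5,940) / 184,756 = 7.0%.

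If each subject is equally likely to be either stage, so that K varies, simulation gives 11-12% for block sizes of 2, 4, 10 and 20. Blocking without stage gives no protection.

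**Step 2: effect on the responder comparison.** Shift = imbalance in Stage I share x gap in responder proportion between stages. A difference of 4 in arms of 10 is 0.40.
- Gap 20 points: 0.40 x 0.20 = 8 points.
- Gap 40 points: 0.40 x 0.40 = 16 points.
- Gap 60 points: 0.40 x 0.60 = 24 points.

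**Step 3: scale.** The 95% half-width for a difference in proportions is 1.96 x sqrt(2p(1-p)/10): 43.8 points at p = 0.5 and 35.1 at p = 0.8. Over all randomisations at K = 10, the SD of the difference in Stage I share is 0.229. At a 40-point gap the stage-driven shift therefore has an SD of 0.229 x 0.40 = 9 points, against a standard error of sqrt(2 x 0.25/10) = 22 points at p = 0.5.

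**Step 4: what adjustment gains or costs.** With half the subjects in each stage and 50% response overall, a gap g accounts for g squared of the variance: 4%, 16% and 36% for gaps of 20, 40 and 60 points. I simulated a continuous change with those shares, 10 v 10, adjusted for stage and for a baseline value assumed uninformative. The mean CI half-width, relative to the unadjusted one, was:
- 4% explained: about 5% wider.
- 16% explained: about 2% narrower.
- 36% explained: about 15% narrower.

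A baseline value that does predict change would improve all three.

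**Step 5: stratified blocks.** With a 50:50 stage mix assumed, blocks within stage hold the difference in stage count to at most 1 (block size 2) or 2 (block size 4). But at 20 subjects the arms are then not 10 v 10 in about 25% and 38% of runs, because of unfinished blocks.

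**The case against.** A reader might infer that the protocol itself makes stage the main predictor of an acute response, so that ignoring it biases the trial and could create or hide a device difference. The documents do not support that. The definitions in section 8.6 give no time frame and refer to elevation, not compression. Section 3.1 names pressure, time and tissue elasticity, not stage. Neither the size nor the direction of a stage effect is stated, and Stage II arms might lose more fluid in absolute terms. The contrast is also narrower than the full Stage 2 definition suggests, because only early Stage II without severe fibrosis is admitted.

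Chance imbalance under randomisation is random error, and a valid unadjusted interval already covers it on average. Only half of the large imbalances would favour FT-SW: about 9% at K = 10 and 7% at K = 6 or 14. Unstratified 1:1 blocks are a defensible choice in a feasibility study aimed at estimation, and if stage predicts only weakly, adjusting for it costs precision.

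All of this stands. It removes any charge of bias and any case for requiring stratification. It does not remove the case for using baseline data already in hand: in a study whose stated focus is estimation, an adjusted difference beside the raw one shows how far the result depends on the allocation that happened to occur.

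**Conclusion.** The plan leaves out a cheap improvement; it does not contain an invalid analysis. It compares raw changes and proportions without the baseline value or stage, and plans no display of stage by arm. The probability of a difference of 4 or more in Stage I count is 14-18% for even totals from 6 to 14, 6-7% for odd totals from 7 to 13, and 11-12% if the mix is left to vary around 50:50. A difference of exactly 4 would shift the responder comparison by 8 to 24 points, but only if the responder proportions of the stages differ by 20 to 60 points, which is an assumption. That is smaller than the 35 to 44 point half-width of the comparison. The influence of baseline values cannot be sized from the documents. Adjustment would not settle how equivalence is to be judged without a margin, which is a separate matter.

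**What to change.** In section 16, for each continuous outcome (limb volume, local tissue water, skin thickness), report the FT-SW minus FT difference in change with a 95% CI. Take it from a linear model with arm, the subject's own baseline value of that outcome (same limb, site and probe) and stage (I or early II) as a second covariate. Give the unadjusted difference beside it, and tabulate stage by arm. Responder proportions by stage within arm may be listed, as description only: cells would hold about 5 subjects, and 3 of 5 has an exact 95% CI of 15% to 95%.

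The cost is wording in section 16 and one or two degrees of freedom out of about 20 (residual 18 falls to 16 with both covariates). If stage proves weakly prognostic and baseline uninformative, the interval widens by about 5% at the equivalent of a 20-point gap. No new data, visits or subjects are needed.

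Generating the blocks separately by stage is optional, and only possible if the list is not yet in use. It would have to be reconciled with the synopsis requirement of at least 10 in each arm, since unfinished blocks can leave 20 subjects unevenly divided.
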